## **5 Protocol Deviation**

Deviations from the protocol, including deviations of inclusion/exclusion criteria will be assessed as 'major' or 'minor' in agreement with Medical Team. Refer to "Guidance Document for Protocol Deviation Reporting and Specifications" for details. All protocol deviations will be appropriately captured in CSR

## **6 General Aspects for Statistical Methods**

In general, metric variables and derived parameters will be presented using descriptive summary statistics including arithmetic mean, standard deviation, median, minimum and maximum.

Categorical variables will be presented using descriptive summary statistics including number of patients and percentages. Percentages of patients will be based on non-missing values. The presentation will be by treatment group. Individual values as well as minimum and maximum will be presented with the same number of decimal places as the raw data. Derived parameter will have as many decimal places as the measured number with the smallest number of decimal places. Descriptive statistics, such as arithmetic/geometric mean and median will be presented with an additional decimal place and standard deviation with two additional decimal places as the raw or derived data. All relevant subject data will be included in the listings; and all subjects entered into the database will be included in subject data listings. SAS 9.4 or any other validated software will be used for analysis purpose and generating Tables, Listings & Figures. P-values less than 0.05 may be reported as statistically significant.

The formatting of the final version of a table, figure, or listing may differ from what is presented in the mock shell or the presentation of the results may be changed, however the key content will remain unchanged. Additional tables, figures, and listings may be generated to supplement the planned output.

## **7 Analysis Population**

ITT/FAS population: Patients randomized (in Arm B) and received at least one full dose of Itolizumab (in Arm A)

Safety population: Patients randomized (in Arm B) and received partial or full dose of Itolizumab (in Arm A)

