Approximately 30 patients are considered sufficient to explore the study objectives and will be included in this study (number of patients may be increased if there is benefit observed in initial cohort of patients. There is no formal sample size calculation estimated).

Method of assigning patient to treatment group:

All eligible patients entering into the study will be randomized in 2:1 ratio to receive the treatment A/ B respectively. A computer derived randomization schedule is planned to be generated using appropriate system e.g. SAS to assign patient to treatment groups. Randomization will be central and appropriate system (e.g. remote telephone based, computer-based email, sealed envelope) will be used to distribute randomization schedule to the site

Note: If the patient is randomised to Arm A and is not initiated itolizumab or not administer one full infusion, is then not considered randomized. The same randomisation code will be used for the subsequent subject in that particular site.

Approximate number of sites:

1-10 sites

7. Treatment

Treatment Intervention and Dose:

Arm A: Best supportive care + Itolizumab

The best supportive care to be given as per the institutions protocol will be administered

(e.g: antivirals /antibiotics/ hydroxychloroquine; oxygen therapy, etc) + **Itolizumab**

Itolizumab

Note: Premedication: Hydrocortisone 100 mg i.v (or equivalent short acting glucocorticoid) and Pheniramine 30 mg per i.v. about 30 ± 10 minutes prior to infusion.

Start at 1.6 mg/kg dose iv infusion, if well tolerated, investigator has the discretion to continue with 1.6 mg/kg dose every 2 weeks or 0.8 mg/kg weekly regimen.

Subsequent dose and frequency can be modified, deferred or stopped if patient recovers as per investigator's discretion. If patients' overall parameters improve (if performed and RT-PCR is negative) further dose need not be given. Total infusion received during study duration can vary from 1 to 4 for each patient.

Arm B: Best supportive care

The best supportive care to be given as per the institutions protocol will be administered

(e.g: antivirals/antibiotics/ hydroxychloroquine; oxygen therapy, etc)

Dosing, Handling and Storage of Itolizumab

- Itolizumab is to be stored in 6R, USP type-1, 10 mL glass vials, refrigerated condition at 2°C to 8°C and is stable at that temperature for 36 months.

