## 3.2 Outcome Measures

### 3.2.1 Primary endpoint

1. Proportion of patients with deterioration of lung function as measured by\*:
  - Stable SpO2 without increasing FiO2
  - Stable PaO2 without increasing FiO2
2. Reduction of endo-tracheal intubation rate, measured as rate of patients needing intubation\*
3. Reduction in proportion of patients who need\*
  - Non-invasive ventilation
  - Invasive mechanical ventilation
  - High flow nasal oxygen
4. Time of duration of mechanical ventilation or time to end of mechanical, measured as elapsed time from the start date of mechanical ventilation to the weaning date, for patients needing intubation\*
5. One-month mortality rate between the two arms\* [ Time Frame: up to 1 month ] 1-month mortality is defined as the ratio of patients who will live after 1 month from study start out of those registered at baseline
6. Change in inflammatory markers like CRP (C-reactive protein) level, d-Dimer, ferritin etc. [ Time Frame: Arm A; baseline, during treatment (Before every dose and 12 to 24 h after every dose) up to 1 month, Arm B: baseline, 12 to 24 h and approx. 7 and 14 days after randomization ]

\* Applicable for both the arm

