## **4 TRIAL DESIGN AND DESCRIPTION**

### **4.1 Trial Design**

It is a Multi-Centric, Open label, Two Arm Randomized, Pivotal Phase 2 Trial to Study the Efficacy and Safety of Itolizumab in COVID-19 complications. Patients who have tested positive for virological diagnosis of SARS-CoV2 infection (PCR) are planned to be randomised for enrolment from various centres in India. All eligible patients entering into the study will be randomized in 2:1 ratio to receive the treatment A/ B respectively.

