#### **4.5 Sample Size, Treatment Assignment, Randomization**

Approximately 30 patients are considered sufficient to explore the study objectives and will be included in this study (number of patients may be increased if there is benefit observed in initial cohort of patients. There is no formal sample size calculation estimated). All eligible patients entering into the study will be randomized in 2:1 ratio to receive the treatment A/ B respectively. A computer derived randomization schedule is planned to be generated using appropriate system e.g. SAS to assign patient to treatment groups. Randomization will be central and appropriate system (e.g. remote telephone based, computer-based email, sealed envelope) will be used to distribute randomization schedule to the site Note: If the patient is randomised to Arm A and is not initiated itolizumab or not administer one full infusion, is then not considered randomized. The same randomisation code will be used for the subsequent subject in that particular site.

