## **8 Demography other baseline Characteristics**

Demographic characteristics including age, gender, race, and ethnicity will be summarized for ITT/FAS populations. Baseline is defined as the last observed value/data before the patient receives study drug for the first time or randomized (in Arm B)

Vital signs such as height, weight, pulse, temperature, respiratory rate, systolic blood pressure, diastolic blood pressure, PaO2/FiO2, FiO2, SpO2, mean arterial pressure & GCS score will be summarized.

Medical history, Physical Examination & concomitant medications will be summarized using counts and percentage. Additionally, prognostic markers and few key laboratory parameters will be summarized.

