## **9 Efficacy Evaluation**

### **Primary Efficacy Evaluation**

Proportion of patients with deterioration of lung function as measured by Stable SpO2 without increasing FiO2 and Stable PaO2 without increasing FiO2 will be summarized using count and

percentage. The difference between two proportion with its 95% Confidence interval and associated p-values may be presented, if p-value is less than 0.05 it can be concluded that there is a statistically significant difference between two proportions.

Reduction of endo-tracheal intubation rate, measured as rate of patients needing intubation will be summarize using descriptive statistics.

Reduction in proportion of patients who need/ Non-invasive ventilation / Invasive mechanical ventilation/high flow nasal oxygen will be summarized using count & percentage.

One-month mortality rate between the two arms will be summarized. The difference between two rates with its 95% Confidence interval and associated p-values may be presented, if p-value is less than 0.05 it can be concluded that there is a statistically significant difference between two-rates.

Change in inflammatory markers like CRP (C-reactive protein) level, d-Dimer, ferritin etc will be summarize with descriptive statistics. Change from Baseline may be presented along with 95% CI.

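### The set called ITT/FAS drops Arm A patients who did not complete a full infusion but keeps every randomised Arm B patient, so the comparison is not intention-to-treat

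*SAP*

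**What the plan says.** SAP 7 defines two sets. The first reads "ITT/FAS population: Patients randomized (in Arm B) and received at least one full dose of Itolizumab (in Arm A"). The second reads "Safety population: Patients randomized (in Arm B) and received partial or full dose of Itolizumab (in Arm A"). An Arm A patient who had only part of an infusion is in the safety set alone. An Arm A patient who was never dosed is in neither set. Every randomised Arm B patient is in both.

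The rule behind this is in Protocol section 6 (method of assigning patients) and again in SAP 4.5: "If the patient is randomised to Arm A and is not initiated itolizumab or not administer one full infusion, is then not considered randomized". The Protocol adds: "The same randomisation code will be used for the subsequent subject in that particular site".

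SAP 9 says of mortality only that "One-month mortality rate between the two arms will be summarized". Neither SAP 9 nor Table 14.2.7 names the analysis set. ITT/FAS is the only set defined other than the safety set, so its use for efficacy is the natural reading, though it is not stated. SAP 9 also allows p below 0.05 on lung function and on mortality to be read as a statistically significant difference. SAP 4.1 describes the study as an "Open label, Two Arm Randomized, Pivotal Phase 2 Trial".

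**The concern.** An intention-to-treat set must not depend on what happens after randomisation. This one does, and only in Arm A. A patient who deteriorates, dies, or has the infusion stopped early leaves the comparison if assigned to Arm A. A patient with the same early course in Arm B stays in. If the removed patients differ in prognosis from the rest, the arms differ even when the drug does nothing.

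Code reuse raises a separate problem. Once an Arm A patient at a site is replaced, staff there can expect the next patient to be assigned to Arm A. That weakens concealment in an open-label trial whose randomisation is otherwise central, and it does so whatever the prognosis of the removed patient.

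Two related passages do not fit together well. One-month mortality is defined "from study start out of those registered at baseline", which arguably includes the removed patients and so conflicts with SAP 7. SAP 8 adds: "Baseline is defined as the last observed value/data before the patient receives study drug for the first time or randomized (in Arm B"). The baseline time point is therefore tied to first dosing in Arm A and to randomisation in Arm B.

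**Working it through.** **No figure to reproduce.** The plan gives about 30 patients without a formal sample size calculation. It gives no mortality rate and no rate of incomplete first infusions. From the documents: 2:1 allocation, hence about 20 v 10, and a two-sided 5% level. The rest is assumed: 30% mortality in both arms, no drug effect, and Fisher's exact test, since SAP 9 names no test.

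**Time at risk.** The schedule in Protocol 8.1 puts randomisation at screening and the first infusion at Day 1 with a ±48-hour window. Screening and baseline may fall on one day. Protocol section 7 sets the infusion at 120 minutes or more, extendable to 8 hours. The exposed period may be only hours.

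**1. Only deaths are removed.** If a share q of Arm A deaths falls before the first infusion is complete, the analysed Arm A rate is p(1−q)/(1−pq), with p=0.30. The last column comes from enumerating all 20 v 10 tables.

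| q | Arm A rate | False advantage (points) | Chance of p<0.05 favouring Arm A |
|---|---|---|---|
| 0 | 30.0% | 0 | 1.89% |
| 1% | 29.8% | 0.2 | 1.95% |
| 5% | 28.9% | 1.1 | 2.19% |
| 10% | 27.8% | 2.2 | 2.55% |
| 20% | 25.5% | 4.5 | 3.47% |
| 30% | 23.1% | 6.9 | 4.76% |

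Total rejection in either direction goes from 3.1% to 5.05%. It starts low because Fisher's test is conservative at this size.

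**2. Removal for any reason.** With a share m of Arm A removed, of whom a proportion r die, the analysed rate is (p−mr)/(1−m).

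| m | r=0 | r=0.3 | r=0.5 | r=1 |
|---|---|---|---|---|
| 2% | 0.6 against | 0 | 0.4 in favour | 1.4 in favour |
| 5% | 1.6 against | 0 | 1.1 in favour | 3.7 in favour |

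Entries are percentage points against or in favour of itolizumab.

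**3. Effect of one death on significance.** Each line adds back one removed Arm A patient who died.

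- 0/20 v 3/10: p=0.030. With 1/21: p=0.087.
- 1/20 v 4/10: p=0.031. With 2/21: p=0.067.
- 3/20 v 6/10: p=0.030. With 4/21: p=0.040, so significance is kept.

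**4. How often this could arise.** If 5% fail to complete the first infusion, the chance that at least one of 20 is removed is 1−0.95^20 = 64%. The chance that a death is removed is 1−(1−0.05×0.3)^20 = 26% if 30% of those removed die, and 40% if half die. If 2% fail, the corresponding figures are 33%, 11% and 18%.

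**The case against.** The strongest reply is that the effect may be negligible. The exposed period can be hours. The exclusion criteria keep out patients already on invasive ventilation and those whose death is judged highly probable. An interrupted infusion can be restarted and still count as full. With about 6 deaths expected among 20 patients (0.30×20), the 20% and 30% rows above mean 1.2 and 1.8 deaths before one infusion ends, which is a lot. Under the null, tables significant for Arm A that lose significance when one death is added have a probability of only 1.09%; times the 26% chance of a removed death, that is about 0.3% (higher if the drug works). All of this stands as a limit on size.

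Direction is not documented either. The one treatment-linked cause of an incomplete infusion that the documents name is infusion reactions, described as expected in Protocol Appendix 3. Such patients may well survive, which would push the bias against itolizumab. Removal of patients too ill to be infused is plausible but is a judgement.

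Nor do the removed patients vanish. Deaths before dosing go in the CRF, everyone in the database is listed, replacements are counted under Table 14.1.1, partly dosed patients stay in the safety set, and deaths are summarised by arm. Table 14.1.2 has a row for randomised patients, though it is unclear whether replaced patients would enter it. None of this puts them back into the efficacy comparison.

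The trial is small and exploratory, with optional p-values. Even so, the plan permits significance statements and uses the ITT name. A modified-ITT set would be a defensible secondary choice if labelled as such, but this one is not, and its condition applies to one arm.

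The mortality-denominator conflict is arguable, since who counts as registered is undefined, and an untreated arm has no first dose on which to anchor baseline.

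**Conclusion.** The concern holds and should be fixed. Following the plan exactly gives a comparison reported as ITT that leaves out patients from one arm on the basis of a post-randomisation event, with no all-randomised efficacy analysis beside it. That conclusion rests on the text alone.

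The size of the bias cannot be derived. Under the assumptions above it runs from about zero to a few percentage points, most plausibly at the low end, and its sign depends on who is removed. Favouring itolizumab seems likelier, but this is not certain. The choice of test also matters: in another assumed case (20% mortality, 10% of Arm A removed, 80% of those dying), total rejection rises from 2.2% to 5.1% with Fisher and from 3.7% to 7.6% with a pooled z test. This is a mislabelled and avoidable asymmetry, together with a weakness in concealment. It is not evidence of a false result.

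**What to change.** - Define ITT in SAP 7 as all randomised patients, analysed by assigned arm and followed from randomisation to Day 30.
- Delete the rule that un-randomises Arm A patients, and the code-reuse sentence, from Protocol section 6 and SAP 4.5. Give each new patient the next unused code.
- Name the ITT set in SAP 9 and Tables 14.2.1 to 14.2.7 for the mortality and respiratory endpoints.
- Reconcile the mortality denominator with that set, using randomisation as the denominator time point in both arms.
- Keep the full-infusion set as a labelled modified-ITT sensitivity analysis.
- Report the Arm A patients not fully infused, with number, reason and Day 30 status, and make sure the randomised row of Table 14.1.2 includes them.

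The cost is amended wording plus Day 30 vital and respiratory status for a few patients. The Day 30 telephone contact in Protocol 8.1 is written for patients who recover or are discharged early, so it would have to be extended to these patients. Including undosed patients slightly dilutes any true drug effect and may make the estimate a little less favourable.

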## **8 Demography other baseline Characteristics**

Demographic characteristics including age, gender, race, and ethnicity will be summarized for ITT/FAS populations. Baseline is defined as the last observed value/data before the patient receives study drug for the first time or randomized (in Arm B)

Vital signs such as height, weight, pulse, temperature, respiratory rate, systolic blood pressure, diastolic blood pressure, PaO2/FiO2, FiO2, SpO2, mean arterial pressure & GCS score will be summarized.

Medical history, Physical Examination & concomitant medications will be summarized using counts and percentage. Additionally, prognostic markers and few key laboratory parameters will be summarized.

## **9 Efficacy Evaluation**

### **Primary Efficacy Evaluation**

Proportion of patients with deterioration of lung function as measured by Stable SpO2 without increasing FiO2 and Stable PaO2 without increasing FiO2 will be summarized using count and

percentage. The difference between two proportion with its 95% Confidence interval and associated p-values may be presented, if p-value is less than 0.05 it can be concluded that there is a statistically significant difference between two proportions.

Reduction of endo-tracheal intubation rate, measured as rate of patients needing intubation will be summarize using descriptive statistics.

Reduction in proportion of patients who need/ Non-invasive ventilation / Invasive mechanical ventilation/high flow nasal oxygen will be summarized using count & percentage.

One-month mortality rate between the two arms will be summarized. The difference between two rates with its 95% Confidence interval and associated p-values may be presented, if p-value is less than 0.05 it can be concluded that there is a statistically significant difference between two-rates.

Change in inflammatory markers like CRP (C-reactive protein) level, d-Dimer, ferritin etc will be summarize with descriptive statistics. Change from Baseline may be presented along with 95% CI.

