Source data is all information, original records of clinical findings, observations, or other activities in a clinical study necessary for the reconstruction and evaluation of the study. Source data are contained in source documents. Examples of these original documents, and data records include: hospital records, clinical and office charts, laboratory notes, memoranda, subject's diaries or evaluation checklists, pharmacy dispensing records, recorded data from automated instruments, copies or transcriptions certified after verification as being accurate and complete, microfiches, photographic negatives, microfilm or magnetic media, x-rays, subject files, and records kept at the pharmacy, at the laboratories, and at medico-technical departments involved in the clinical study.

Location of Data

All records and documents pertaining to the study will be maintained in the permanent files of the Investigator and will be available for inspection by the authorized party at any time.

Statistical Analysis

In general, continuous variables is summarized using descriptive statistics such as mean, standard deviation, 95% confidence interval (CI), minimum, and maximum. Categorical variables are summarized using proportions (counts and percentages). All statistical tests will be performed at 5% level of significance (two-sided test) and p-value<0.05 considered statistically significant (if necessary). All statistical analysis will be performed using SAS® (version 9.4 or higher) system software (SAS Institute Inc., USA)/or R/or EAST/or NCSS software.

11.Administrative Procedures

Ethics and Good Clinical Practice

This research will be carried out in accordance with the clinical research guidelines established by the basic principles defined in the revised New Drugs and Clinical Trials 2019, India and the principles enunciated in the Declaration of Helsinki [Ethical Principles for Medical Research Involving Human Subjects, revised, October 2013]. The investigator is responsible for overall activities at the center in accordance with Indian ICH-GCP guidelines, current New Drugs and Clinical Trials 2019 and ethical guidelines for biomedical research on human subjects issued by ICMR.

Interim study report - Data will be provided to DSMB (constituted prior to first patient screened) on a periodic basis. Based on DSMB recommendation, interim clinical study report may be prepared and submitted to DCGI/regulatory agencies.

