### **4.3 Inclusion Criteria**

1. Male or female adults above 18 years (not tested in children yet)
2. Informed consent for participation in the study
3. Confirmed virological diagnosis of SARS-CoV2 infection (RT-PCR)
4. Hospitalized due to clinical worsening of COVID-19 infection
5. Oxygen saturation at rest in ambient air  $\leq 94\%$
6. Patients who are in moderate to severe ARDS as defined by PaO2/Fio2 ratio of < 200 or more than 25% deterioration from the immediate previous value.
7. Baseline serum ferritin level  $\geq 400$  ng/mL or IL-6 levels greater than 4 times ULN, if known

Note: Either of Inclusion number 6 or 7 is required for inclusion of the patient into the study. Since there is logistical delay in getting results in time, biomarker data as inclusion criteria may be used if already known.

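### Mortality and lung-function proportions are compared without adjustment for baseline severity and the 2:1 schedule names no stratum, so at 20 v 10 a chance severity imbalance would make the one observed estimate hard to interpret

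*SAP*

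**What the plan says.** - **Analysis (SAP 9, Primary Efficacy Evaluation).** For the stable SpO2 and stable PaO2 proportions: "The difference between two proportion with its 95% Confidence interval and associated p-values may be presented". One-month mortality has a parallel sentence. No covariate, stratum, model, test or interval method is named. Intubation and ventilation or high-flow need are summarised only.
- **Randomisation (SAP 4.5; same text in Protocol section 6).** "A computer derived randomization schedule is planned to be generated using appropriate system e.g. SAS to assign patient to treatment groups". Patients are "randomized in 2:1 ratio to receive the treatment A/ B respectively". No stratification factor, block size or minimisation is given. If an Arm A patient does not receive one full infusion, "The same randomisation code will be used for the subsequent subject in that particular site".
- **Entry (SAP 4.3).** Everyone must be hospitalised for clinical worsening with room-air SpO2 of 94% or less. Beyond that, "Either of Inclusion number 6 or 7 is required for inclusion of the patient into the study". Criterion 6 is PaO2/FiO2 below 200 or a fall of more than 25%. Criterion 7 is ferritin of at least 400 ng/mL or IL-6 above 4 times the upper limit.
- **Baseline data.** Protocol 8.1 schedules PaO2/FiO2 at screening. SAP 8 lists it among the variables to be summarised and gives it no role in the efficacy comparison.
- **Size (SAP 4.5).** "Approximately 30 patients are considered sufficient to explore the study objectives", and "There is no formal sample size calculation estimated". The number may be raised if benefit is seen in the first patients.

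**The concern.** Patients with and without PaO2/FiO2 below 200 probably differ in their risk of death and respiratory failure. With about 10 controls, neither the design nor the analysis limits how unevenly these two kinds of patient fall between the arms. If the arms come out uneven, the raw difference mixes the drug effect with case mix. An adjustment chosen after the imbalance has been seen will look selective. SAP 4.1 calls the trial pivotal, and an early apparent benefit may lead to more patients being enrolled, so a chance imbalance favouring Arm A could also influence that decision.

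**Working it through.** **Inputs from the documents.** N about 30, ratio 2:1, so 30 × 2/3 = 20 in Arm A and 30 × 1/3 = 10 in Arm B. The documents give no power, event rate or effect size, so there is no sample-size figure to reproduce.

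**Assumptions.** Severe means baseline PaO2/FiO2 below 200. The number severe is K = 9, 12 or 15 of 30 (30%, 40%, 50%). Failure risks are assumed and shown as a range.

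**Step 1: chance of imbalance.** With x severe patients in Arm B, P(x) = C(K,x) C(30−K,10−x) / C(30,10). The difference in severe share, A minus B, is (K−x)/20 − x/10, which moves in steps of 15 points.

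| K | x giving 30 points or more | Either direction | Favouring Arm A |
|---|---|---|---|
| 9 | 0–1 or 5–9 | 0.204 | 0.104 |
| 12 | 0–2 or 6–10 | 0.235 | 0.118 |
| 15 | 0–3 or 7–10 | 0.245 | 0.123 |

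**Step 2: effect on the raw difference, and on variance.** With no drug effect, an imbalance of 0.30 shifts the raw difference by 0.30 × (severe risk − other risk). The Mantel-Haenszel difference is Σ w_k d_k / Σ w_k, with w_k = n_Ak n_Bk / (n_Ak + n_Bk), where d_k is the difference in stratum k. Its variance against the raw one was simulated under unstratified allocation, with 30% to 50% severe.

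| Severe / other risk | Shift at 30 points | Variance, MH v raw |
|---|---|---|
| 0.2 / 0.2 (not prognostic) | 0 | about 4% higher |
| 0.3 / 0.2 | 3 points | about 2% higher |
| 0.2 / 0.05 | 4.5 points | 2–4% lower |
| 0.3 / 0.1 | 6 points | 2–4% lower |
| 0.5 / 0.2 | 9 points | about 7% lower |
| 0.6 / 0.2 | 12 points | 13–14% lower |
| 0.7 / 0.2 | 15 points | 21–23% lower |
| 0.7 / 0.1 (extreme) | 18 points | 36–38% lower |

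**Step 3: scale.** The null standard error is √[p(1−p)(1/20 + 1/10)]. With half of patients severe, risks 0.2/0.05 give p = 0.125 and √(0.109 × 0.15) = 0.128. Risks 0.5/0.1 give p = 0.30 and √(0.21 × 0.15) = 0.177. The matching shifts are 4.5 and 12 points, so in both cases the shift is smaller than one standard error.

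**Step 4: type I error.** In simulation with half of patients severe and risks from 0.2/0.05 to 0.7/0.1, Fisher's test on the raw table rejected in 1.5% to 3.5% of trials. Among trials with an imbalance of 30 points or more favouring Arm A, it rejected in about 4% to 9%.

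**The case against.** The best defence is that randomisation makes the raw comparison valid. Chance imbalance is part of the sampling error that the interval already describes, and steps 3 and 4 bear this out. The trial is described as exploratory, the tests are optional, and adjustment with 10 controls is a preference rather than a requirement. If enrolment grows, the problem shrinks: at N = 60 with half severe, a 30-point imbalance has a probability of about 5%. All of this stands. It limits the point to how the realised estimate can be interpreted.

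Four stronger readings are tempting, and the documents or the figures do not support them.

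- *That patients may enter on raised ferritin alone.* Ferritin or IL-6 replaces only the ARDS criterion; hypoxia and hospitalisation for worsening apply to all. SAP 4.4 also excludes invasive ventilation and patients judged highly likely to die, so the severity range is cut at both ends.
- *That every binary primary endpoint is compared raw.* Only lung function and mortality have a planned comparison. The non-invasive ventilation and high-flow shells (SAP 14.2.3 and 14.2.6) are already restricted to patients on that support at baseline.
- *That low baseline PaO2/FiO2 must predict failure on stable PaO2.* SAP 12 defines stability relative to the patient's own baseline, so the link is uncertain.
- *That adjustment is sure to buy a substantial gain in precision.* The gain depends wholly on assumed risks, and it becomes a small loss when the factor is weak.

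**Conclusion.** The point holds in a limited form. The two planned binary comparisons ignore a baseline severity measure that the trial already collects, and no stratification factor is named. At 20 v 10, an imbalance of 30 points or more in severe share has a probability of 20% to 25%, about half of it favouring Arm A. It would move the raw difference by about 5 to 15 points over most of the assumed risks. A reader might infer that this biases the trial or inflates its error rate; it does neither unconditionally. What is lost is a credible reading of the one result the sponsor will have, and possibly some precision. The case is strongest for mortality.

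The imbalance figures rest on an assumed 30% to 50% severe, and the shift and variance figures on assumed event risks, because the documents give none. The small sample limits precision more than the lack of adjustment does.

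**What to change.** **Analysis.** In SAP 9, prespecify the Mantel-Haenszel risk difference stratified by baseline PaO2/FiO2 below 200 (yes/no) for one-month mortality and the stable SpO2 and stable PaO2 proportions, with the raw difference beside it. Name a small-sample interval or an exact stratified test; the usual Mantel-Haenszel interval covered only about 91% to 93% in simulation at this size. Take the stratum from the last value before randomisation in both arms, because the SAP 8 baseline for Arm A runs up to the first dose. One two-level factor is enough with 10 controls. SAP 1 allows revision before database lock. The cost is a paragraph and a few lines of code, plus a variance about 2% to 4% higher if the factor proves weakly prognostic or not prognostic.

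**Randomisation (optional, for patients not yet randomised).** Use permuted blocks within the same factor, which adds one data item when the code is requested. Do this only if the SAP 4.5 rule on reusing a code for the next patient at the site is removed or confined to the same stratum. Otherwise a code can pass to a patient in the other stratum and undo the balance.

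**What this leaves open.** Neither change repairs the exclusion and replacement of Arm A patients who do not receive a full infusion (SAP 4.5 and 7). That is a separate and larger threat to comparability.
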